13 DATA HANDLING & RECORD KEEPING

13.1 Direct Access

The Investigator/Institution will permit trial-related monitoring, audits, IRB review, and regulatory inspections by providing direct access to the source data/documents as needed.

13.2 Confidentiality & Security

All information disclosed or provided by the Sponsor (or any company/institution acting on their behalf), or produced during the study, including, but not limited to, the Study Protocol, the CRFs, the Instructions for Use and the results obtained during the course of the study, is confidential. The Investigator or any person under his/her authority agrees to undertake to keep confidential and not to disclose the information to any third party without the prior written approval of the Sponsor.

However, the submission of this Study Protocol and other necessary documentation to the Ethics Committee (IRB) is expressly permitted, the IRB members having the same obligation of confidentiality.

The Sub-Investigators, if employed, shall be bound by the same obligation as the Investigator. The Investigator shall inform the Sub-Investigators of the confidential nature of the Usability Study.

The Investigator and the Sub-Investigators shall use the information solely for the purposes of the Study, to the exclusion of any use for their own or for a third party's account.

All data to Laborie will be confidential and all subject identifiers will be blacked out before being sent to Laborie. Documents will be kept in a secure location and all digital information will be kept following HIPAA and local government regulations.

13.3 Data Handling

A list of individuals will be maintained who are authorized to make any changes to the data. Data will be reviewed by the Sponsor (outside of monitoring personnel), and requests for clarification and/or corrections will be made through the monitor. Once the review is conducted, the database will be considered clean and ready for analysis. Missing values will remain missing, i.e. no attempt will be made to input missing values and only observed values will be used in data analyses and presentations.

13.4 Case Report Form (CRF) & Source Documents

All study staff will be trained on the protocol requirements and questionnaire completion. It is the responsibility of the Investigator to maintain adequate and accurate questionnaires and CRFs designed by Laborie to record all observations and other data pertinent to the clinical investigation. All questionnaires and CRFs should be completed in their entirety in a neat, legible manner to ensure accurate integration of data. Should a correction be made, the information to be modified must not be overwritten. The corrected information will be transcribed by the authorized person on the questionnaire. Source document worksheets for recording data will be created as agreed upon by the sponsor or the site as required. Data from the source documents should be entered into the CRF after each subject's visit. The anonymized UDS data files (DTA files) requested by the sponsor for each patient, to confirm the quality of the study. A unique subject code will be assigned to each subject based on the site number (100) and sequential subject number (i.e. 100-001). The investigator is responsible for maintaining subject identifying information. CRF's will be treated as source data in the event

that the original information is entered in the CRF first (and no source document worksheet is utilized for that data point).

13.5 Record Retention

An investigator or sponsor shall maintain the records required by 21 CFR Part 812.140 during the investigation and for a period of 2 years after the latter of the following two dates: The date on which the investigation is terminated or completed, or the date that the records are no longer required for purposes of supporting a premarket approval application or a notice of completion of a product development protocol. The Investigator must maintain confidential all study documentation, and take measures to prevent accidental or premature destruction of these documents. All essential documents from the Investigator will be kept in the Investigator binder. All sponsor essential documents will be kept in the study master file. The investigator and sponsor shall also maintain a record of their location of the respective essential documents. If the Investigator's personal situation is such that archiving can no longer be ensured by him/her, the Investigator shall inform the Sponsor and the relevant records shall be transferred to a mutually agreed upon designee.

13.6 Performance Monitoring

Monitors will periodically check questionnaire data to ensure all fields are entered as far as possible and inquire as to whether any usability issues are being encountered as the study progresses.

14 MONITORING, AUDITING, AND INSPECTING

14.1 Study Monitoring Plan

The Investigator agrees to provide reliable and accurate data, and all information requested by the study protocol (with the help of any questionnaire, other appropriate instruments) in an attributable, legible, contemptuous, original, accurate, and complete form according to the instructions provided and to ensure direct access to source documents to Sponsor representatives. Any changes to the soured data shall be traceable and not obscure the original entry.

The Sponsor of this Study is responsible to Health Authorities for taking all reasonable steps to ensure the proper conduct of this study protocol with regards to ethics, protocol compliance, integrity and validity of the data recorded on the CRF and questionnaires. Thus, the main duty of the Monitoring Team is to help the Investigator and the Sponsor maintain a high level of ethical, scientific, technical and regulatory quality in all aspects of the study.

At regular intervals during the study, the site will be contacted, through monitoring visits, letters or telephone calls, by a representative of the Monitoring Team to review study progress, Investigator and subject compliance with study protocol requirements, and any emergent problems. The monitoring plan will describe the frequency, extent, and nature of monitoring.

14.2 Auditing and Inspecting

For the purpose of ensuring compliance with the study protocol, Good Clinical Practice and regulatory requirements, the Investigator should permit inspection by applicable regulatory body authorities. This investigation will not include audits conducted by the Sponsor.

The Investigator agrees to allow the inspectors to have direct access to his/her study records for review, being understood that these personnel are bound by professional secrecy, and as such will not disclose any personal identity or personal medical information.

The Investigator will make every effort to help with the performance of the inspections, giving access to all necessary facilities, data, and documents.

As soon as the Investigator is notified of a future inspection by the authorities, he will inform the Sponsor and authorize the Sponsor to participate in this inspection.

The confidentiality of the data verified and the protection of the subjects should be respected during these inspections.

Any result and information arising from the inspections by the regulatory authorities will be immediately communicated by the Investigator to the Sponsor. The Investigator shall take appropriate measures required by the Sponsor to take corrective actions for all problems found during the inspections.

15 DEVIATIONS

All departures from the approved protocol shall be documented by the Investigator. All deviations will be recorded on the subject CRF, and a deviation report will be sent to Laborie and the ethics board, as required. Timelines for notification will be subject to ethics board standard operating procedures. Deviations will be reviewed and signed off by the sponsor. If deviations are observed/reported that significantly affect or have the potential to significantly affect human subject protection or reliability of the trial results, then LABORIE will conduct a root cause analysis and implement appropriate corrective and preventative actions.

16 AMENDMENTS

If there are any changes to the protocol during the application of the study or during the length of the clinical study in progress, the IRB will be notified for review. During an ongoing study if an amendment is made to the protocol the amended protocol will be sent to the applicable institution within the timelines required. The Investigator should not implement any deviation from, or changes to the clinical protocol without agreement by the sponsor and prior review and documented approval/favourable opinion from the IRB of an amendment, except when necessary to eliminate an immediate hazard(s) to a clinical study subject. In some instances, an amendment may require a change to the Informed Consent Form. The investigator must

receive an IRB approval/favourable opinion concerning the revised Informed Consent Form prior to implementation of the change.

17 STUDY ADMINISTRATION

17.1 Funding Source and Conflicts of Interest

Laborie will be the sponsor and the financial details are covered in the Investigator Agreement.

17.2 Subject Stipends or Payments

Subjects will be offered a \$40 USD stipend for their participation in the study to offset the cost of parking and/or meals required during their clinic visit.

The Sponsor has covered this study by means of an insurance covering bodily injury or property damage arising out of the clinical trial. The certificate of insurance evidencing the coverage, insurance company, policy number and the sum insured are provided in the Study's File.

17.3 Committees

A Data Monitor Committee will not be utilized in this study based on the evaluation of the level of potential risks.

17.4 Study Timetable

PROPOSED STUDY TIMELINE	TOTAL DURATION (WEEKS)	ACTUAL DATES
PROPOSED SITE TRAINING & INITIATION PHASE	1	July 2018
PROPOSED RECRUITMENT (1 st subject in to last subject out)	8	July- September 2018
PROPOSED DATABASE LOCKOUT	1	October 2018
PROPOSED STUDY REPORT COMPLETION	3	October 2018
TOTAL (WEEKS / MONTHS)	-	
ESTIMATED COMPLETION (QUARTER)	Start Q4 FY2018	End of October 2018

18 ETHICS AND REGULATORY APPROVAL

This study will not begin until the appropriate approvals from the IRB have been obtained. Any additional requirements imposed by the IRB will be followed. This study will be conducted in compliance with all international laws and regulations, and national laws and regulations of the countries in which the usability study is performed, as well as any applicable guidelines.

19 PUBLICATION POLICY

The results of the study may be submitted for publication, whether peer-reviewed or marketing materials. Publication rights and details are covered in the Investigator Agreement, there may be other authors involved in the creation of the publication.

20 ATTACHMENTS

20.1 Informed Consent Documents

- TDOC-NXT-01-ICF - Informed Consent Form

20.2 Investigator's Brochure

- TDOC-NXT-01-IB T-DOC NXT Investigator's Brochure

20.3 Case Report Forms

- TDOC-NXT-01- CRF1Case Report Form 1
- TDOC-NXT-01- CRF2Case Report Form 2
- TDOC-NXT-01- CRF3Case Report Form 3
- TDOC-NXT-01- CRF4Case Report Form 4
- TDOC-NXT-01- CRF5Case Report Form 5

T-DOC® NXT Study

STUDY NUMBER:

TDOC-NXT-01

STUDY NAME:

T-DOC® NXT Clinical Investigation:

*Assessing the Performance, Safety and Usability of our Next Generation T-DOC®
NXT Catheter for Performing Urodynamic Studies*

NCT NUMBER:

NCT03615001

DOCUMENT:

STATISTICAL ANALYSIS PLAN

DOCUMENT VERSION & DATE:

Version 1.0

November 8, 2018

	T-DOC® NXT Clinical Study Statistical Analysis Plan	TDOC-NXT-01-SAP	Version 1.0	Page 1 of 6
--	--	-----------------	-------------	-------------

CLINICAL STUDY STATISTICAL ANALYSIS PLAN

DEVICE:

T-DOC® NXT Air-Charged Urodynamic Catheters

STUDY NUMBER:

TDOC-NXT-01

STUDY NAME:

T-DOC® NXT Clinical Investigation:

*Assessing the Performance, Safety and Usability of our Next Generation T-DOC® NXT Catheter for
Performing Urodynamic Studies*

Version 1.0

November 8, 2018

SIGN-OFF

Statistician	Print Name		Date	12 Nov. 2018
	Signature			

This document has been reviewed by LABORIE (Refer to Entropy PRC# 023486).

Contents

Introduction	3
Study Objectives and Endpoints	4
Analysis Populations	5
Primary Endpoint	5
Exploratory Endpoints.....	6

Introduction

The purpose of this statistical analysis plan (SAP) is to provide clarification about the statistical considerations and methods to be implemented for the analysis of data from the T-DOC NXT clinical study. This statistical analysis plan is based on protocol version 1.0 (TDOC-NXT-01-PR-V1.0). The protocol clearly describes the study endpoints, but the hypothesis testing procedures and criteria for study success requires additional details. The SAP is written by an independent statistician [REDACTED] with no access to or knowledge of accumulating trial data. Any revisions to the SAP will be made prior to database lock and reasons for such revisions will be described in the final clinical study report.

Study Objectives and Endpoints

The following are the objectives and endpoints of the TDOC-NXT-01 clinical study:

OBJECTIVES	ENDPOINTS
Primary	
To confirm the T-DOC® NXT vesical and abdominal catheters as a safe and effective means of measuring urodynamic pressure in adults.	The primary endpoint will be measured by recording the clinician safety and effectiveness rating for each patient on their CRF. The clinician will indicate whether the T-DOC® NXT vesical and abdominal catheters are safe and effective for measuring urodynamics pressure in patients who enrolled and completed the urodynamic procedure.
Exploratory Objective 1	
To evaluate the usability of the device by collecting clinical user feedback and evaluating the following subjective measures using defined ordinal scales: ease of use, ease of insertion, presence of artefacts, stability of the tracing, perceived time savings, ease of voiding around catheter, presence of use errors and overall satisfaction.	The usability performance endpoint will be captured in a questionnaire format. The trained clinical users will rate the T-DOC® NXT performance on a scale of 1-5 on the study outcome questionnaire.
Exploratory Objective 2	
To explore whether the newly designed, smaller sized T-DOC® NXT catheters causes undue discomfort based on subjective subject feedback regarding the discomfort and pain level, for those able to communicate such feedback.	This exploratory endpoint will be measured by collecting patient feedback regarding the level of discomfort and pain experienced during their Urodynamic test using the Numeric Pain Rating Scale (NPRS). Patients capable of providing feedback on a scale, will grade their discomfort/pain at 5 or lower, on the NPRS from 0 ("No Hurt") to 10 ("Hurts worst").

Analysis Populations

All subjects enrolled and completed the urodynamic procedure will be considered in the final analysis. Enrolled subjects who do not undergo the urodynamic procedure or begin the urodynamic procedure but do not complete it (for any reason determined by the investigator to be unrelated to the T-DOC® NXT catheters) will not be included in the final analysis and can be replaced.

If any CRFs are found to be incomplete, the study monitor will follow-up as to the reasoning. If for some reason a clinical user is unable to complete their questionnaire, the questions they have completed will be included in the analysis.

Primary Endpoint

The primary safety and effectiveness endpoint is a binary clinician response after each UDS study using the T-DOC® NXT catheter to determine whether the ability to measure UDS pressure was clinically adequate (success) or inadequate (failure).

In the statistical analysis plan, the null hypotheses for the safety and effectiveness endpoints are designed to rule out success rates $\leq 75\%$.

The allowable Type I error (α) for each hypothesis will be 5% (1-sided), and the Type II error is calculated to be 10% (90% power).

Safety and effectiveness will be evaluated separately via the following sets of hypotheses:

Primary Hypothesis for Safety

H_0 : Safety Success Rate is $\leq 75\%$

versus

H_A : Safety Success Rate is $> 75\%$

Primary Hypothesis for Effectiveness

H_0 : Effectiveness Success Rate is $\leq 75\%$

versus

H_A : Effectiveness Success Rate is $> 75\%$

The study will be declared a success if both null hypotheses for safety and efficacy are ruled out.

Exploratory Endpoints

Exploratory Objective 1 for Usability Performance

This exploratory endpoint was collected to reflect that the goal of qualitatively describing users' interactions with the device as described in regulatory guidance for usability testing (*FDA's guidance- 'Applying Human Factors and Usability Engineering to Medical Device's, 2016*). A clinical user who completed the T-DOC® NXT clinical study, shall rate the T-DOC® NXT catheter usability performance on a scale of 1-5 for the clinical user questionnaire, comparing their experience with use of their currently used urodynamics catheter on per urodynamic day basis.

Since there will be only daily responses from one user for each of the questions, the results are thus not well-suited to statistical analysis and hypothesis testing is not appropriate. Instead, descriptive statistics will be used to summarize and analyse the results of each question, including: ease of use, ease of insertion, presence of artefacts, presence of coughs/Valsalva response, measurements and tracings of urethral pressure profiles, stability of the tracing, perceived time savings, ease of voiding around catheter, presence of errors and overall satisfaction.

The reported value in the usability performance survey will be analysed using proportions of levels and cumulative proportions of groupings at 95% confidence interval. This includes levels (1 to 5), "Yes and no", "better, same or worse" and any other questions related to usability.

Additionally, the results will be plotted over time to observe the trend as the study continues (preferably a line plot with daily responses over time).

Exploratory Objective 2 for Discomfort/Pain

To satisfy this exploratory endpoint for subject experience, a categorical response variable using the Numeric Pain Rating Scale (NPRS) from 0 ("No Hurt") to 10 ("Hurts worst") will be used. Subjects will grade their discomfort/pain on the scale from 0 ("No Hurt") to 10 ("Hurts worst"). Descriptive statistics will be used to summarize and analyse the results of questionnaires completed per patient for questions about pain during insertion, during test and during removal of the T-DOC® NXT catheters.

The reported value in the patient survey will be analysed using proportions of levels and cumulative proportions of groupings at 95% confidence interval. This includes levels (0 to 10) and "Yes and No".

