4.3 Claims and Intended Performance

- The T-DOC® NXT catheter causes minimal discomfort during insertion, during the test, and removal
- Adverse Event Claims as per results
- Subjective claims:
 - The T-DOC® NXT catheters are safe and effective for use on adult patients
 - The T-DOC® NXT catheters are easy to use
 - The T-DOC® NXT catheters are easy to set-up / zero
 - The T-DOC® NXT catheters are easy to insert
 - The T-DOC® NXT catheters have consistent/stable tracings
 - The T-DOC® NXT catheter has adequate subtracted pressures

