4.4 Assessment of Risks and Adverse Device Effects

Risks to the subject will be no greater than those of a standard UDS test. Subjects may experience temporary discomfort upon insertion of the catheters. Test duration may be slightly longer than a standard test while assessment of the study materials is being made, and so discomfort and inconvenience associated with an extended test duration may occur.

UDS testing exposes subjects to risks of urethral instrumentation which can result in infection, urethral trauma and pain (Winters *et al.* 2012). Other risks can include transient discomfort during or following the procedure, transient dysuria or bleeding (hematuria) following the procedure, or urinary tract infection, which occurs in 2-4% of subjects (Chapple, MacDiarmid & Patel, 2009).

In conclusion, the overall residual risks associated with the use of T-DOC® NXT catheters within this study set-up, are acceptable when weighed against the benefits, and are no different than the risks when using other UDS catheter technologies. The sponsor team has also established that patients are subjected to no more than minimal risk since an IDE is not required for this study (Ref: TDOC-NXT-01 - Risk Determination). Lastly, UDS is a widely-performed procedure on subjects requiring specialized management for urinary incontinence/retention problems, as

recommended by the ICS (Abrams *et al.*, 2013), and is useful in characterizing LUT function, identifying causes of symptoms and quantifying related pathophysiological processes (Rosier PF., 2013). Thus, the clinician must weigh the risks and benefits as to whether the UDS test offers additional diagnostic value beyond symptom assessment, physical examination and other diagnostic testing (Winters *et al.*, 2012).

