7.6 Subject Withdrawal

Subjects may withdraw voluntarily from the study or the investigator may terminate a subject's participation (see below). The Investigator will notify the sponsor when a subject is withdrawn from the study (and if possible why), and this will be recorded on the subject's CRF and withdrawal form. Subjects who withdraw from the trial will be allowed to be replaced by another subject.

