10 PATIENT SAFETY

10.1 Definitions

10.1.1 Adverse Events:

Any untoward medical occurrence in a subject, whether or not related to the investigational medical device.

10.1.2 Adverse Device Effect:

Any adverse event related to the use of an investigation medical device.

10.1.3 Device Deficiency:

Inadequacy of a medical device with respect to its identity, quality, durability, reliability, safety or performance

10.1.4 Serious Adverse Event:

An adverse event that:

1. Led to a death;
2. Led to a serious deterioration in health of a patient, user, or others that:
 - a. Results in a life-threatening illness or injury;
 - b. Results in a permanent impairment of a body structure or body function;
 - c. Requires in patient hospitalization or prolongation of existing hospitalization;
 - d. Results in medical or surgical intervention to prevent life-threatening illness or injury or permanent impairment to body structure or a body function;
3. Led to foetal distress, foetal death or a congenital abnormality/birth defect.

10.1.5 Unanticipated Adverse Device Effect:

Any serious adverse effect on health or safety or any life-threatening problem or death caused by, or associated with, a device, if that effect, problem, or death was not previously identified in nature, severity, or degree of incidence in the investigation protocol or application, or any other unanticipated serious problem associated with a device that relates to the rights, safety, or welfare of subjects.

10.1.6 Unanticipated Serious Adverse Device Effect (USADE):

Serious adverse device effect which by nature, incidence, severity or outcome has not been identified in the current version of the risk analysis report.

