12.5 Analysis Plan

A Statistical Analysis Plan containing the details of the analyses and hypothesis testing will be finalized prior to database lock. All subjects who complete the UDS study will be considered in the final analysis. Data will be analysed as discussed in Section 12.1 above.

If any CRFs are found to be incomplete, the study monitor will follow-up as to the reasoning. If for some reason a clinical user is unable to complete their questionnaire, the questions they have completed will be included in the analysis. Data will be monitored as the study progresses, please refer to Section 7.7 for details about suspension or premature termination.

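### The safety co-primary has no all-exposed population: subjects who stop for a reason judged unrelated to the catheters leave its denominator and may be replaced, which can bias the safety rate upward.

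*SAP*

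**What the plan says.** The SAP (Analysis Populations) has one set for everything: "All subjects enrolled and completed the urodynamic procedure will be considered in the final analysis". Two kinds of enrolled subject are left out: those who never undergo the procedure, and those who "begin the urodynamic procedure but do not complete it (for any reason determined by the investigator to be unrelated to the T-DOC® NXT catheters". Such subjects "will not be included in the final analysis and can be replaced". The SAP's table of objectives and endpoints likewise ties the clinician's safety and effectiveness rating to patients who completed.

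The protocol points the same way. Section 12.5 states: "All subjects who complete the UDS study will be considered in the final analysis". Section 7.6 adds: "Subjects who withdraw from the trial will be allowed to be replaced by another subject". Section 13.3 rules out imputation and uses observed values only.

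Safety is tested separately. Protocol 12.1.2 defines it as the clinician's binary rating of the device's safety after each study, compared with 75%, and the SAP requires both null hypotheses to be rejected for study success. Under protocol 9.2 the physician overseeing the case makes the safety interpretation. There is one arm and no blinding (6.1, 12.4). Neither document defines an all-exposed safety set or a sensitivity analysis for excluded subjects.

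**The concern.** A safety rate should normally cover everyone exposed. Here an exposed subject can leave the safety denominator because of a relatedness judgement made after exposure by the unblinded clinical side, which also supplies the rating. The protocol's own adverse event definition (10.1.1) does not depend on relatedness: "Any untoward medical occurrence in a subject, whether or not related to the investigational medical device". The tested safety endpoint is therefore narrower than the plan's own concept of a safety event.

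A test that stops early is a plausible place for an inadequate safety rating. If such subjects are dropped and completers take their places, the safety rate is overstated. The same set is used for the pain scores, although protocol 4.3 plans the claim that "The T-DOC® NXT catheter causes minimal discomfort during insertion, during the test, and removal". Pain is exploratory and descriptive, so the main stake is the safety co-primary, where one or two subjects can decide the result.

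**Working it through.** **Inputs.** Null rate 75% and assumed true rate 96% (protocol 12.1, 12.3); one-sided alpha 5% (protocol 2.2.1 and 12.3, SAP Primary Endpoint); 20 to 40 subjects (protocol 7.4). The number of excluded exposed subjects and their failure rate are not in the documents and are assumed below.

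**The plan's own figure.** With n = 20, at least 19 successes are needed: P(X ≥ 19 | 0.75) = 0.024. Power is 0.96^20 + 20 × 0.96^19 × 0.04 = 0.442 + 0.368 = 81.0%, against the stated 81%. With n = 30 (27 needed) and n = 40 (35 needed) the exact power is 96.9% and 99.5%, against the stated 96% and 99%. The exact test is thus the right tool for what follows.

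**Effect on the decision.** The Clopper-Pearson lower limit for x successes in n is the alpha quantile of Beta(x, n − x + 1). At alpha = 5%, compared with 75%:

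| Analysed as planned | Excluded subjects restored as failures | Excluded subjects restored as rated adequate |
|---|---|---|
| 19/20: 78.4%, pass | one: 19/21: 72.9%, fail | 20/21: 79.3%, pass |
| 20/20: 86.1%, pass | two: 20/22: 74.1%, fail | 22/22: 87.3%, pass |
| 27/30: 76.1%, pass | one: 27/31: 72.9%, fail | 28/31: 76.8%, pass |

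The middle column is the worst case and the right-hand column the best. In between, 20/20 with two restored subjects, one of them a failure, gives 21/22 (80.2%), still a pass. The 19/20 and 27/30 rows start on the pass boundary, so they show the most fragile results, not typical ones.

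**Effect on the rate.** Suppose completers succeed at 96%, a share d of exposed subjects is excluded, and a share f of those are safety failures. The all-exposed rate is (1 − d) × 0.96 + d × (1 − f).
- d = 5%: 96.0% at f = 4%, 93.7% at f = 50%, 91.2% at f = 100%.
- d = 10%: 96.0%, 91.4% and 86.4%.

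At f = 4%, the completers' own failure rate, there is no bias.

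**Effect on type I error.** Suppose the true all-exposed rate is exactly 75%, and a share h of would-be failures is excluded and replaced. The analysed rate is 0.75 / (0.75 + 0.25 × (1 − h)). At h = 20% this is 0.75 / 0.95 = 78.9%. Type I error then rises from 2.4% to 5.6% (n = 20), from 3.7% to 9.7% (n = 30) and from 4.3% to 12.6% (n = 40). At h = 10% it is 3.7%, 6.1% and 7.5%.

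**The other limit.** Protocol 12.1.2 states a 97.5% one-sided limit for safety, while protocol 2.2.1 gives 95% and the SAP 5% one-sided. At 97.5%, 19/20 still passes (75.1%) and 19/21 still fails (69.6%); 20/20 passes (83.2%) and 20/22 fails (70.8%). But 27/30 already fails as planned (73.5%), so the third row of the table applies only at 95%.

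**The case against.** The strongest reply is that the rule reaches only stops unrelated to the catheters. A reader might infer from protocol 4.4, which says that the risks "are no different than the risks when using other UDS catheter technologies", that a test stopped for pain or bleeding at insertion could be set aside as procedural. The text does not support that. The sentence compares catheters and refers to risks from using the T-DOC NXT; it does not call such events unrelated to it. Section 4.4 links discomfort to catheter insertion, and section 10.1.2 counts any event related to use of the device as an adverse device effect. Read properly, such a stop falls outside the exclusion. Misclassification remains possible, but the rule does not prescribe it.

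A second reply concerns size. A clinician who has judged a stop unrelated may well rate the device's safety adequate, and then nothing reverses. This stands, and the reversals must be read as worst case.

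A third reply is that safety information is not lost: adverse events go on the CRF and the AE form (10.2, 11.4), serious events are reported (10.3), and withdrawals are documented, with the reason if possible (7.6). This is true, but it does not repair the tested denominator, and the SAP plans no adverse event analysis.

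**Conclusion.** The point holds as a gap in the safety denominator. A stated rule lets an exposed subject leave a tested safety endpoint on an unblinded judgement made after exposure, and no all-exposed analysis stands beside it. At 20 subjects, one or two excluded failures are enough to turn a fail into a pass.

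The size is conditional. It depends on how many exposed subjects are excluded and how they would have been rated, and the documents give neither. Three stronger readings go too far:

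- That following the rule necessarily biases the rate upward. It does so only if excluded exposed subjects fail more often than completers.
- That every non-completer is dropped. The SAP exclusion covers only stops judged unrelated. Catheter-related stops fall outside it, yet the inclusion sentence and the endpoint table mention completers only, so their handling is unclear.
- That every excluded subject was exposed and is replaced. Beginning the procedure is not defined as catheter insertion, though nothing confines it to the time before insertion. Replacement is permitted, not required.

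**What to change.** Before database lock, amend the SAP as follows:

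- Define a safety population of every subject in whom insertion of any T-DOC NXT catheter was attempted, regardless of completion or judged relatedness. These subjects are not replaceable for the safety denominator.
- Test the safety hypothesis in this set with the clinician's safety rating on the CRF, and add a sensitivity analysis that counts a missing rating as a failure.
- List each exclusion with its reason. Report adverse events and all available NPRS scores in this set.
- Keep the current rule for effectiveness only.
- Reconcile the confidence level for safety across protocol 2.2.1, protocol 12.1.2 and the SAP.

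The cost is SAP wording and a second denominator; the CRFs and AE form already exist. The safety rate may be slightly less favourable, and the two co-primaries may have different N. Because the SAP is dated November 2018 and recruitment was planned for July to September 2018, ratings for subjects who already stopped may be missing and not recoverable, which is why the sensitivity analysis is needed. The SAP allows revisions up to database lock, with reasons given in the final report.
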